A comparison of the baseline characteristics between patients with missing data for the primary effectiveness variable and those without missing data are provided below. These test are intended to determine if there is evidence of not missing at random and if there is, to provide a remedy such that the missing data can be assumed to be missing at random for those patients for which imputation is planned. An initial analysis indicated that baseline weight, BMI, and site and core laboratory exercise durations were statistically significant. The weight variable was considered of lower importance, but the exercise duration could impact anaerobic threshold (AT, the primary effectiveness variable) and therefore indicated that, strictly speaking, the data are not missing at random. A review of the data indicated that the vast majority of exercise times exceeded 6-7 minutes and that subjects with short exercise times were less likely to show an improved AT regardless of treatment group. On that basis, any patient missing the 24 week PVO2 and/or 24 week AT was assigned a worst case score. This is similar to patients who had an event, i.e, patients who died or had an intervention (LVAD, heart transplant, or surgery to correct CHF) at a time that could be considered the reason why the data for 24 weeks was missing. There were 10 Active and 4 Control patients who had events prior to the 24 week visit and there were 3 Active and 6 Control patients who had an event between 24 and 50 weeks such that the event was considered the reason for missing the 24 week CPX. The inclusion of patients with missing 24 week data and a baseline core laboratory exercise time of less than 6.5 minutes results in 5 Active and 8 Control patients added to the worst score assignment list. The cumulative result is that 18 Active and 18 control patients had either the lowest AT value from any previous visit assigned, or if all AT values were missing for previous visits, the lowest AT value recorded for any randomized patient. These patients are indicated in Table IX.1 below as Imputation Case 6.

After removing the 13 cases with missing 24 week data and an exercise time less than 6.5 minutes, the baseline characteristic comparison between patients with missing and non-missing data at 24 weeks or baseline are presented in the following tables.

Table VIII.1 Baseline Demographics – Quantitative Variables - Compare Patients with Missing 24 Week AT data with those Not Missing 24 Week Data

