Table VIII.2 Baseline Demographics and Medical History Categorical Variables - Compare Patients with Missing 24 Week AT data with those Not Missing 24 Week Data

Variable	Missing n/N (%)	Non Missing n/N (%)	P- value ¹
Male	58/80 (72.50)	251/348 (72.13)	1.0000
Ethnicity (White)	52/80 (65.00)	244/348 (70.11)	0.4207
CHF Etiology (Ischemic)	32/80 (40.00)	115/348 (33.05)	0.2426
Prior MI	44/80 (55.00)	207/348 (59.48)	0.5292
Prior CABG	30/80 (37.50)	138/348 (39.66)	0.7998
Prior PCI	30/80 (37.50)	139/348 (39.94)	0.7058
Diabetes	38/80 (47.50)	155/348 (44.54)	0.7088
NYHA (site) (Class IV)	11/80 (13.75)	37/348 (10.63)	0.4334

¹Two-sided Fisher's exact test.

Table VIII.3 Baseline Medications - Compare Patients with Missing 24 Week AT data with those Not Missing 24 Week Data

Medication	Missing n/N (%)	Non-Missing n/N (%)	P-Value ¹
Angiotensin converting enzyme inhibitor (ACEi)	58/80 (72.50)	243/348 (69.83)	0.6856
Angiotensin receptor blocker (ARB)	18/80 (22.50)	85/348 (24.43)	0.7733
ACEi or ARB	72/80 (90.00)	318/348 (91.38)	0.6660
Beta Blocker	72/80 (90.00)	328/348 (94.25)	0.2060
Loop Diuretic	76/80 (95.00)	316/348 (90.80)	0.2701
Second Diuretic	9/80 (11.25)	22/348 (6.32)	0.1489
Aldosterone Inhibitor	35/80 (43.75)	162/348 (46.55)	0.7096
Hydralazine	7/80 (8.75)	20/348 (5.75)	0.3122
Nitrates	27/80 (33.75)	121/348 (34.77)	0.8970
Calcium Channel Blocker	4/80 (5.00)	23/348 (6.61)	0.7994
Anti-arrhythmic	4/80 (5.00)	61/348 (17.53)	0.0031

¹Two-sided Fisher's exact test.

Only anti-arrhythmic medication use was statistically significantly difference between the missing and non-missing groups. The non-missing group had the higher rate of anti-arrhythmic medication use.

Table VIII.4 Baseline Cardiopulmonary Exercise (Core Laboratory) - Compare Patients with Missing 24 Week AT data with those Not Missing 24 Week Data

Variable	Control Mean (SD) N Med (Min, Max)	Optimizer Mean (SD) N Med (Min, Max)	P –value
Duration (minutes) ³	11.22 (3.50) 80 10.48 (4.92, 18.82)	11.47 (3.29) 347 11.65 (2.73, 20.13)	0.3570 ¹
Peak SBP (mmHg) ⁴	139.9 (24.3) 80 140 (96, 210)	139.1 (26.2) 343 140 (72, 240)	0.7116 ¹
Peak HR (bpm) ⁵	124.0 (20.4) 80 123.5 (72, 173)	121.1 (20.3) 346 121 (72, 176)	0.2372 ¹
Peak VO2 (ml/kg/min) ⁶	14.69 (2.99) 78 14.65 (8.4, 21.7)	14.73 (3.00) 347 14.80 (8.5, 23.0)	0.8189 ¹
Peak RER ⁷	1.13 (0.11) 79 1.12 (0.89, 1.52)	1.13 (0.09) 347 1.12 (0.97, 1.57)	0.7702 ²
AT (ml/kg/min) ⁸	11.00 (1.99) 64 10.6 (7.4, 15.6)	10.95 (2.25) 344 10.7 (5.3, 17.0)	0.7541 ¹

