¹Two-sided Wilcoxon rank sum test.

²Two-sided unequal variance two-sample t-test.

³One non-missing patient did not have a core lab report on exercise duration.

⁴Five non-missing patients did not have core lab report of baseline peak SBP.

⁵Two non-missing patients did not have core lab report of peak heart rate.

⁶Two missing patients and one non-missing patient did not have a core lab report of peak VO2.

⁷One missing patient and one non-missing patient did not have a core lab report of peak RER.

⁸Sixteen missing patients and four non-missing patients did not have a core lab report of AT.

Exercise testing was not statistically significantly different between the missing and non-missing patients after deleting missing patients with less than 6.5 minute of baseline exercise duration. These tests do not provide evidence that the missing at random assumption for the imputations below is violated.

IX. Imputation Methods

There are several methods of imputation that could be applied to missing data based on what data are missing and the relationships of the missing observations to data that are present. The proposed method of imputation depends on the amount of data that are present for any given subject as summarized in the following table, and detailed below.

Table IX.1 Imputation Cases from Statistical Analysis Plan

CASE	Baseline		6 Month Follow-Up		Imputation Method	Patients in Case	
	Peak VO2	AT	Peak VO2	AT		Treatment	Control
0	Present	Present	Present	Present	None	159	153
1	Present	Present	Present	Absent	Stochastic regression based on PVO2 and RER at 6M	8	9
2	Present	Absent	Present	Present	Stochastic regression based on PVO2 and RER at Baseline	10	2
3	Present	Absent	Present	Absent	Stochastic regression based on Δ PVO2 and RER	1	0
4	Present	Present	Absent	Absent	Propensity Matching and Random Selection	18	29
5	Present	Absent	Absent	Absent	Propensity Matching and Random Selection	1	2
6	Patients died, had an event, or had missing data and baseline duration <6.5 minutes ¹					18	18

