¹A comparison of exercise duration between patients with missing and non-missing 24 week AT data indicated that subjects missing 24 week data with short baseline exercise times (<6.5 minutes) were possibly not missing at random. Assigning these patients worst case values and removing them from the missing patient comparison resulted in no statistically significant differences between the patients with missing and non-missing 24 week AT values demonstrating that there is no violation in the missing at random assumption.

a. Regression Imputations

For the patients in groups 1-3 above, the regression analysis of the completed cases resulted in the coefficients presented in the table below.

Table IX.2 Regression Results for Imputation

Imputation Case 1	Intercept	Coefficient of PVO2 (6 Mo.)	Coefficient of RER (6 Mo.)	Root Residual Mean Square
6-Mo AT Missing Control	9.138	0.538	-5.502	1.170
6-Mo AT Missing Optimizer	4.163	0.597	-1.945	1.132
Imputation Case 2	Intercept	Coefficient of PVO2 (BL)	Coefficient of RER (BL)	Root Residual Mean Square
Baseline AT Missing Control	6.421	0.619	-3.888	1.176
Baseline AT Missing Optimizer	6.534	0.613	-4.096	1.127
Imputation Case 3	Intercept	Coefficient of ΔPVO2 (6 Mo.)	Coefficient of ΔRER (6 Mo.)	Root Residual Mean Square
Baseline and 6-Month AT Missing Control	-0.075	0.571	-4.212	1.300
Baseline and 6-Month AT Missing Optimizer	-0.118	0.614	-1.499	1.270

The imputed value is obtained by generating a standard normal value, z, and then applying the formula below for cases 1 and 2.

$$AT = z*s + a + b_1 * PVO2 + b_2 * RER$$

Where s is the root mean square from the regression (an estimate of the standard deviation of the AT value), a is the intercept, b₁ is the coefficient for PVO2 and b₂ is the coefficient for RER. The equation for case three is similar with the difference that the AT term being estimated and the PVO2 and RER values are differences between 24 weeks and baseline.

b. Propensity Score Imputation (Imputation Cases 4 and 5)

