The patients who had both PVO2 and AT at 24 week missing were assigned to Imputation Case 4. In addition to the one patient missing AT at baseline, and PVO2 and AT at 24 weeks, one patient missing PVO2 and AT at baseline and PVO2 at 24 weeks and a second patient missing PVO2 and AT at baseline were added to Imputation Case 5. Because there were only three patients in Case 5, these were added to Case 4 for propensity score assignment and subsequent imputation. The random selection based on the propensity score quintile replaced only the missing values for any patient. For the purposes of

modeling missingness, patients in the combined Cases 4 and 5 were assigned a missingness indicator and all other patients were assigned an indicator that data were not missing. The propensity scores were assigned modeling the missingness of the combined Cases 4 and 5 by non-parsimonious logistic regression. The model estimates are provided in the table below.

Table IX.3 Non-parsimonious Model for Propensity Score Imputation

Baseline Covariate*	Estimated Coefficient	P-value
Age	-0.0237	0.1129
Treatment Group	0.2644	0.0914
Gender (Female)	0.00976	0.9569
CHF Etiology (Ischemic)	0.0584	0.7557
Diabetic	-0.1579	0.3209
LVEF (Site)	0.0215	0.3739
Baseline MLWHFQ	-0.0134	0.0635
NYHA (Class IV)	0.0503	0.8356
Baseline PVO2	0.0204	0.7150
Baseline RER	0.5316	0.7460

*Only covariates that have data for at least 90% of patients will be used and missing data will be imputed by substituting the median by treatment group for the missing variable. Propensity score covariates can have no missing values.

The random selection was done from quintiles of patients with actual non-missing data based on propensity scores and the numbers of missing, assumed non-missing (patients not in Case 4 or 5) and actual non-missing patients (the subset of patients not in Cases 4 or 5 with non-missing data) are presented in the table below.

Table IX.4 Distribution of Patients by Treatment and Propensity Score Quintile

Quintile	Missing n/N (%)	Not Case 4 or 5	Not Missing
1	2/50 (4.00)	84/378 (22.22)	75/348 (21.55)
2	12/50 (24.00)	74/378 (19.58)	67/348 (19.26)
3	11/50 (22.00)	74/378 (19.58)	70/348 (20.11)
4	8/50 (16.00)	78/378 (20.63)	72/348 (20.69)
5	17/50 (34.00)	68/378 (17.99)	64/348 (18.39)

This table demonstrates that there is a more than ample set of patients with complete data from which the patients with missing data can obtain values in each quintile. The random selection is done with replacement.

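### The report claims that baseline comparisons demonstrate missing at random, which they cannot do and Table VIII.3 contradicts; the imputation model omits two flagged variables and the planned worst-case analysis is not shown

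*Combined protocol and SAP*

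**What the plan says.** All places are in the Statistical Analysis Report unless the protocol is named.

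- **Section VIII, opening text.** "An initial analysis indicated that baseline weight, BMI, and site and core laboratory exercise durations were statistically significant". Because duration could affect AT, the report concludes that "strictly speaking, the data are not missing at random". It gives worst scores to 13 patients (5 Optimizer, 8 Control) with missing week-24 data and a baseline duration under 6.5 minutes, then repeats the comparison.
- **Table VIII.3, after that step.** The row reads "Anti-arrhythmic 4/80 (5.00) 61/348 (17.53) 0.0031", and the text below it says "Only anti-arrhythmic medication use was statistically significantly difference between the missing and non-missing groups".
- **End of Section VIII.** "These tests do not provide evidence that the missing at random assumption for the imputations below is violated".
- **Table IX.1 footnote.** The reassignment "resulted in no statistically significant differences between the patients with missing and non-missing 24 week AT values". The footnote then presents this as "demonstrating that there is no violation in the missing at random assumption".
- **Table IX.3.** The propensity model for Cases 4 and 5 has ten covariates: age, treatment, gender, etiology, diabetes, site LVEF, MLWHFQ, NYHA IV, peak VO2 and RER (last row "Baseline RER 0.5316 0.7460"). A note limits covariates to those available for at least 90% of patients.
- **Protocol Section IX.D.** Where data are missing, a worst-case analysis is to be performed for the primary efficacy endpoint, with missing controls counted as successes and missing treatment patients as failures.

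**The concern.** Missing at random means that, given the observed data, missingness does not depend on the unseen week-24 AT. Comparing baselines can speak against missing completely at random. It cannot establish missing at random, because the quantity in question was never seen.

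Section VIII also labels dependence on exercise duration, an observed baseline, as a failure of missing at random. Such dependence is compatible with the assumption provided duration is in the imputation model. The natural response to a baseline difference is to condition on that variable. Table IX.3 does not do so for duration or for anti-arrhythmic use. Weight and BMI, also flagged initially, are absent too.

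At stake is the reliance placed on the imputed responder analyses. The whole-population ITT result is already non-significant (combined P=0.3142, Section XII). The exposed claim is the subgroup with EF≥25 and NYHA III, the only one that Section XII declares significant at 0.025.

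**Working it through.** **1. The footnote's premise.** Two-sided Fisher test on 4/80 against 61/348 gives P=0.0031, as printed. The odds ratio is (4×287)/(76×61) = 0.25 (Wald 95% CI 0.09 to 0.70). So a significant difference did remain after the reassignment.

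**2. Who is in the 80 and the 348.** From Table IX.1:
- Cases 1 to 5: 17+12+1+47+3 = 80.
- Cases 0 and 6: 312+36 = 348.
- 80+348 = 428, so nobody was dropped.

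Two cross-checks agree. Sixteen of the 80 lack baseline AT, which equals Cases 2, 3 and 5 (12+1+3). Four of the 348 also lack it; Case 0 requires it, so those four must be in Case 6. By count, the 13 short-exercise patients were therefore moved into the non-missing group, although Section VIII speaks of removing them.

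**3. What that does to duration.** Table VIII.4 (its columns are headed by treatment, but the Ns show missing against non-missing) gives 11.22 (SD 3.50, n=80) against 11.47 (SD 3.29, n=347), Wilcoxon P=0.3570. A Welch t-test from those summaries, as an approximation, gives P=0.56. The difference is −0.25 min, SE √(3.50²/80 + 3.29²/347) = 0.43, 95% CI −1.09 to 0.59; 80% power exists only for about 2.80×0.43 = 1.2 min. The mean duration of the 13 is not given, so I assume 4.5 to 6.4 min:
- 13 returned to the missing group: difference −1.46 to −1.12 min, P about 0.0015 to 0.008.
- 13 left out altogether: P about 0.22 to 0.30.

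**4. Eligibility of the omitted covariates.** Anti-arrhythmic use is known for 80+348 = 428 of 428 and core-lab duration for 80+347 = 427 of 428. Both pass the 90% rule. The smallest P in Table IX.3 is 0.0635 (MLWHFQ).

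**5. Reach of the model.** Cases 4 and 5: Optimizer 18+1 = 19, Control 29+2 = 31, total 50. Share of Cases 1 to 6: 50/116 = 43%.

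**6. Sensitivity of the subgroup claim.** Responders are as the report defines them (AT up by ≥20%).
- Pooling Table XII.3b by the report's formula with denominators 109 and 97: mean difference 0.1209, within-variance 0.00242, between-variance 0.000395, total 0.00242 + 1.1×0.000395 = 0.00285, |z| = 0.1209/√0.00285 = 2.26, P=0.0118. This matches the report. Four of the ten imputations individually exceed 0.025 (0.0440, 0.0265, 0.0613, 0.0311).
- Observed (Table XIV.4b): 4/69 Control, 17/83 Optimizer. Without an observed change: 97−69 = 28 and 109−83 = 26.
- Imputed responders average 9.1−4 = 5.1 of 28 and 23.4−17 = 6.4 of 26.
- Illustration with assumed rates, 6/28 and 3/26: 10/97 against 20/109. Difference 8.0 points, SE 4.8, z = 1.67, Wald P=0.048; one-sided Fisher, the report's own test, P=0.075.
- Protocol worst case, treating all 54 as missing: (4+28)/97 = 33.0% against 17/109 = 15.6%, a difference of −17.4 points, favouring control.

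**The case against.** **The wording error is local.** Section VIII ends with the cautious statement and openly reports the anti-arrhythmic difference. True, but the footnote still needs correction, since it says something different and stronger.

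**The anti-arrhythmic finding may be chance.** Tables VIII.1 to VIII.4 hold 43 tests. If independent, the chance of at least one P≤0.0031 is 1−(1−0.0031)^43 = 12%, and 0.0031 does not pass Bonferroni (0.05/43 = 0.0012). It also concerns 80 patients, whereas Table IX.3 models missingness in 50. The number of users among those 50 is not given; for 0 to 4 users, Fisher P against the other 378 runs from 0.0002 to 0.15. No passage links anti-arrhythmic use to change in AT, and omitting a predictor of missingness that is unrelated to outcome does not bias an imputation. All of this stands.

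**Duration was dealt with.** Worst scores were assigned, and peak VO2 and RER are in the model. Even with the 13 left out altogether, duration is not significant in step 3. This stands in part: duration was handled by a rule rather than by modelling, and the printed P=0.3570 partly reflects where the 13 were placed.

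**Other checks on the missing data exist.** Case 6 departs from missing at random for 36 patients, and completed-case results are given. But Case 6 assigns low values to 18 patients in each arm, so it does not test differences between arms, and the completed-case results vary no assumption about the missing patients.

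**The illustration does not measure the covariate omission.** Correct. Its rates are chosen and cover all 54 subgroup patients without an observed change, including any in Cases 1 to 3 and 6. Six of 28 controls is within the imputed range (3 to 7); only 3 of 26 Optimizer patients falls outside it (5 to 8).

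**Conclusion.** The footnote is wrong on two counts: it claims a demonstration that baseline tests cannot give, and it states an absence of differences that Table VIII.3 contradicts. The Case 4 and 5 model leaves out two eligible variables that the report itself flagged, and the worst-case efficacy analysis in protocol Section IX.D does not appear in Sections XII to XIV.

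A reader might infer more, and the documents do not support it:
- That missing at random is shown to be violated. It is neither shown nor refuted.
- That the omitted covariates biased the result towards Optimizer. Neither size nor direction can be computed without patient data.
- That the subgroup result is overturned. The illustration and the worst case show dependence on assumptions about 54 patients, not what those patients did.
- That the whole-population conclusion changes. It was already non-significant.

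These findings rest on the printed counts, on the group composition inferred in step 2, and on treating all 54 subgroup patients without an observed change as missing.

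**What to change.** 1. Reword the Table IX.1 footnote to match the cautious close of Section VIII, and acknowledge the anti-arrhythmic difference. State that the 348 include Case 6.
2. Add baseline core-lab exercise duration and anti-arrhythmic use to the Case 4 and 5 propensity model, and consider weight and BMI. Keep the 6.5-minute worst-score rule; dropping it is a separate and debatable choice.
3. Report the worst-case analysis in protocol Section IX.D, with a delta-adjusted tipping-point table on the responder rate, for the whole population and for both subgroups.

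The data are already collected. The cost is re-running ten imputations for each of ITT, FASA and FASB with their two subgroups, and labelling the revised model as a post hoc change. The subgroup claim may become less favourable.

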²Pseudo-sites were used in this analysis and are defined in Table 4a.

Table VI.8 Summary of Study Site Comparability¹ for Baseline Medications.

Variable	P-value for Treatment	P-value for Study Site ²	P-value for Site by TRT Interaction
ACEi	0.1089	0.5171	0.0226
ARB	0.4673	0.3345	0.4238
ACEi +/- ARB	0.0518	0.0191	0.0261
B-Blocker	0.5372	0.1887	0.6063
Diuretic	0.4026	0.9576	0.4637
Second Diuretic	0.0122	0.0035	0.0161
Aldosterone Inhibitor	0.1551	0.7007	0.2385
Antiarrhythmic	0.2260	0.3131	0.5036
Hydralazine	0.5334	0.9813	0.7634
Nitrates	0.8873	0.3973	0.6726
Ca Channel Blocker	0.2411	0.3480	0.9998

¹Analysis by logistic regression.

²Pseudo-sites were used in this analysis and are defined in Table 4a.

Table VI.9 Summary of Study Site Comparability¹ for Baseline Cardiopulmonary Exercise

Variable	P-value for Treatment	P-value for Study Site ²	P-value for Site by TRT Interaction
Duration (minutes)	0.4822	0.0022	0.2157
Peak SBP (mmHg)	0.7493	<0.0001	0.5936
Peak HR (bpm)	0.4134	0.0223	0.4897
Peak VO2 (ml/kg/min)	0.9894	0.6534	0.5938
Peak RER	0.7288	0.0020	0.9477
AT (ml/kg/min)	0.9690	0.3116	0.4726

¹Analysis by general linear models analysis of variance with Type III sums of squares.

²Pseudo-sites were used in this analysis and are defined in Table 4a.

Because several baseline variables were significantly different between study sites, study pseudo-site will be used as a possible covariate in multivariate analyses below.

VII. Study Populations

The analysis populations are the intention to treat (ITT) consisting of all subjects randomized. The full analysis set A (FASA), consisting of all randomized patients but excluding patients who never received a study treatment (there were 7 Optimizer and 1 Control patient excluded in this population). The full analysis set B (FASB) consisting of all randomized patients excluding patients who did not receive a study treatment or had no study follow-up (there were 7 Optimizer and 6 Control patients excluded from this population). The population of completed cases (CC) consisting of all patients with a 24 week endpoint. The final population is the per protocol (PP) consisting of all CC patients who did not have a protocol violation that would

substantially affect study outcomes. Imputation by the methods described below is used to provide outcomes for effectiveness for subjects without outcomes in the ITT and FAS populations.

VIII. Comparison of Patient with Missing and Non-Missing Data

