X. Primary Safety Analysis

The primary safety analysis evaluated the composite event rate of all cause mortality and all cause hospitalization at 50 weeks. The statistical hypothesis is that the proportion of subjects in the treatment group where an event occurs by the 50 weeks will be non-inferior to the proportion of subjects where an event occurs by the 50 weeks in the control group. The statistical hypothesis to be tested is:

$$H_0: \pi_t > \pi_c + \delta$$

vs.

$$H_1: \pi_t \leq \pi_c + \delta$$

where $\delta=0.125$ (clinically insignificant difference) and π_c is the event rate in the control group and the π_t is the event rate in the treatment group. The statistical test to be used shall be the Blackwelder (1982) non-inferiority test and will be evaluated based on the intent-to-treat subject population.

The events comprising the composite primary safety endpoints are provided in the table below for all patients, for patients grouped by core lab ejection fraction (< 25 or ≥ 25), and patients grouped by core lab ejection fraction and NYHA (equal to 3 or not).

Table X.1 Primary Safety Events (Deaths or All Cause Hospitalizations) for the ITT Population

Group	Control n/N (%)	Optimizer n/N (%)	P-Value ¹
All	103/213 (48.36)	112/215 (52.09)	0.0348
BL EF ² <25	50/99 (50.50)	56/98 (57.14)	0.2041
BL EF ² \geq 25	53/113 (46.90)	56/117 (47.86)	0.0399
BL EF ² <25 & NYHA \neq 3	9/14 (64.29)	7/11 (63.64)	0.2484
BL EF ² <25 & NYHA=3	41/85 (48.24)	49/87 (56.32)	0.2805
BL EF ² \geq 25 & NYHA \neq 3	11/16 (68.75)	4/8 (50.00)	.00696
BL EF ² \geq 25 & NYHA=3	42/97 (43.30)	52/109 (47.70)	0.1219

¹One-sided Blackwelder's test for non-inferiority with $\delta = 0.125$

²One Control patient did not have a baseline core laboratory ejection fraction

There were 103 events in the control group and 112 events in the Optimizer group by 50 weeks. If one applies the Blackwelder test to the ITT population, assuming those lost to follow-up did not have an event, the rate in the control arm is $103/213 = 0.4836$ and in the test arm is $112/215=0.5209$. The difference is 0.0374 and the Blackwelder z-statistic is -1.8143 which corresponds to a P-value of 0.0348. The upper one-sided 95% confidence limit is 11.68 which is below the delta of 12.5. Under this test, the primary safety endpoint is met.

Recognizing that 6 control patients and 7 Optimizer patients either died or withdrew early with no follow-up beyond the screening examination, the modified ITT

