The analysis of the combined imputations for FASB (EF \geq 25 and NYHA=3) resulted in a z=-2.1549 with corresponding P=0.0156.

These imputation analyses by ITT, FASA, or FASB all resulted in similar outcomes. The whole population does not demonstrate statistical significance at a 0.025. The sub group of patients with baseline EF \geq 25 results in a P-value less than 0.05, but slightly above the 0.025 value and the sub-group with EF \geq 25 and NYHA=3 achieves statistical significance with P<0.025.

XIII. Secondary Effectiveness Analyses

The mean AT and PVO2 at Baseline, 24 weeks and 50 weeks for the CC population are given in the table below.

Table XIII.1a Mean AT and PVO2 at Study Time Points

Variable	Time	Control Mean (SD) N Med (Min, Max)	Optimizer Mean (SD) N Med (Min, Max)	P-value
AT	Baseline	10.97 (2.18) 207 10.73 (5.40, 17.05)	10.95 (2.24) 201 10.60 (5.29, 16.92)	0.9528 ¹
	24 Week	10.96 (2.20) 158 10.83 (6.24, 19.61)	10.87 (2.45) 169 10.49 (5.01, 19.82)	0.7346 ¹
	24 Week Difference From Baseline	-0.14 (2.14) 154 -0.23 (-4.99, 9.34)	-0.14 (2.23) 159 -0.25 (-6.47, 8.94)	0.5040 ³
	50 Week	10.92 (2.49) 148 10.78 (4.10, 20.93)	11.10 (2.56) 163 10.92 (5.40, 21.83)	0.5471 ¹
	50 Week Difference From Baseline	-0.14 (2.64) 146 -0.35 (-6.45, 10.66)	0.01 (2.59) 156 -0.30 (-5.43, 12.25)	0.3158 ³
PVO2	Baseline	14.71 (2.92) 211 15.02 (8.54, 22.61)	14.73 (3.06) 214 14.48 (8.43, 23.02)	0.9245 ¹
	24 Week	14.54 (3.56) 169 14.47 (6.30, 27.95)	14.94 (3.62) 179 14.47 (7.63, 27.49)	0.3008 ¹
	24 Week Difference From Baseline	-0.41 (2.90) 168 -0.50 (-7.68, 11.60)	0.24 (3.16) 179 -0.04 (-8.17, 11.69)	0.0242 ³
	50 Week	14.59 (3.87) 159 14.47 (6.88, 29.75)	14.72 (3.51) 172 14.47 (8.12, 30.67)	0.7394 ¹
	50 Week Difference From Baseline	-0.44 (3.01) 152 -0.58 (-7.80, 12.06)	-0.08 (3.47) 164 -0.21 (-6.87, 17.45)	0.2330 ³

¹Two-sided equal variance Student's t-test.

²Two-sided unequal variance Student's t-test

³One-sided equal variance Student's t-test

The responder analyses for the CC population at 24 and 50 weeks are provided in the table below.

Table XIII.1b Responder Analysis (20% or Greater improvement from Baseline) at Study Time Points

Variable	Time	Control n/N (%)	Optimizer n/N (%)	P-value ¹
AT	24 Week	18/154 (11.69)	28/159 (17.61)	0.0932
	50 Week	21/146 (14.38)	37/156 (23.72)	0.0275
PVO2	24 Week	23/168 (13.69)	31/179 (17.32)	0.2169
	50 Week	24/158 (15.19)	31/172 (18.02)	0.2944

¹One-sided Fisher's exact test

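### The propensity draw in Section IX.b leaves out baseline AT, and its 348 donors described as having actual data include 36 patients with assigned worst-case scores; the net effect on the subgroup results is unknown

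*Combined protocol and SAP*

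**What the plan says.** Section IX of the Statistical Analysis Report sorts patients into Cases 0 to 6 (Table IX.1). Case 0 is fully observed. Cases 1 to 3 are filled by stochastic regression, and Cases 4 and 5 by random draw. Case 6 (death, event, or missing data with a baseline exercise time under 6.5 minutes) is assigned a worst-case AT under Section VIII.

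For Cases 4 and 5, Section IX.b fits a logistic model for being missing. Table IX.3 lists ten baseline covariates, including peak VO2 and RER but not AT. Values are drawn with replacement within quintiles of the fitted score. On donors the report says: "The random selection was done from quintiles of patients with actual non-missing data based on propensity scores". Table IX.4 counts 348 of them, and the text after it states that "there is a more than ample set of patients with complete data". The draw supplies a value, not a change from baseline: "The random selection based on the propensity score quintile replaced only the missing values for any patient".

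Table XIII.1a gives the observed 24-week AT (mean, SD, N, median, range) as "10.96 (2.20) 158 10.83 (6.24, 19.61") for Control and "10.87 (2.45) 169 10.49 (5.01, 19.82") for Optimizer.

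The footnote to Table IX.1 treats non-significant baseline comparisons as showing that missing at random (MAR) holds. The last sentence of Section VIII is more careful and claims only no evidence against it.

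**The concern.** The report's responder is a patient whose 24-week AT is at least 20% above that patient's own baseline AT. A draw that takes little account of baseline breaks the link on which the endpoint is built: a low-baseline patient becomes too likely to respond, and a high-baseline patient too likely to show a large fall. Separately, if donors include Case 6, an assigned penalty score is passed to patients who did not meet the Case 6 criteria, and the description tells the reader otherwise.

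These ten data sets are the efficacy analysis of Section XII. They also feed the EF≥25 result (reported combined P = 0.0260, next to the 0.025 threshold) and the EF≥25/NYHA III result (P = 0.0118), on which the report's positive message rests.

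**Working it through.** **1. Reproducing the 348.** Table IX.1, both arms: Case 0 159+153 = 312; Case 1 17; Case 2 12; Case 3 1; Case 4 47; Case 5 3; Case 6 18+18 = 36. The sum is 428. Without Cases 4 and 5: 428 − 50 = 378, as in Table IX.4. Without Cases 1 to 3 as well: 378 − 30 = 348 = 312 + 36. Case 6 is therefore 36/348 = 10.3% of the pool. The draw touches 50/428 = 11.7% of patients. By the text of Section IX.b, two of the three Case 5 patients lack baseline values, so the 24-week argument applies chiefly to the 47 in Case 4.

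**2. The other reading of 348.** 348 is also the number with a 24-week peak VO2 (169+179, Table XIII.1a). Cases 2 and 3 would then count as non-missing, so at least 12+1 = 13 non-missing patients would lack baseline AT. Footnote 8 of Table VIII.4 counts four, and 16 in the missing group, which matches Cases 2+3+5 = 12+1+3. That excludes the peak VO2 reading, if Tables VIII.4 and IX.4 use the same 348. On either reading only 158+169 = 327 patients have an observed 24-week AT, so at least 348 − 327 = 21 donors do not.

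**3. Were assigned scores drawn?** In Table XII.2a the EF≥25 Optimizer 24-week minimum is exactly 4.10 in ITT4 and ITT6 and in no other imputation. The lowest observed 24-week AT is 5.01. A Case 6 patient's own score is fixed and would appear in all ten. Regression could produce 4.10 to two decimals at most 8 patients × 10 × 0.01 × 0.399/1.132 = 0.28 times, even if every Optimizer Case 1 draw were centred there. A donated worst-case score fits best.

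**4. How much baseline information the score carries.** Baseline AT is present for 207+201 = 408/428 = 95.3% (Table VI.4), above the report's own 90% rule. The nearest proxy is peak VO2. Coefficient × approximate SD gives age 0.296, treatment 0.264, LVEF 0.141, MLWHFQ 0.306, diabetes 0.158, peak VO2 0.061, RER 0.051; the squares sum to 0.303. The share of peak VO2 is 0.061²/0.303 = 1.2% (1.6% if binary terms are coded 0/1), taking covariates as independent.

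Completer correlation, from (s₀² + s₁² − s_d²)/(2s₀s₁):
- Control: (2.18² + 2.20² − 2.14²)/(2×2.18×2.20) = 0.52
- Optimizer: (2.24² + 2.45² − 2.23²)/(2×2.24×2.45) = 0.55

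The SDs come from slightly different Ns, so roughly 0.5 is as precise as this allows.

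**5. Possible size of the lost correlation.** Under bivariate normality, P(24-week ≥ 1.2 × baseline) for Control has mean 10.96 − 1.2×10.97 = −2.20 and variance 2.20² + 1.44×2.18² − 2.4ρ×2.18×2.20. At ρ = 0 the probability is 0.260, and at ρ = 0.52 it is 0.177. Optimizer gives 0.266 and 0.176. Control completers actually respond at 18/154 = 11.7%, so the approximation runs high.

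**6. Patients with no follow-up.** Section X says "6 control patients and 7 Optimizer patients either died or withdrew early with no follow-up beyond the screening examination", and Section VII says of FASB that "there were 7 Optimizer and 6 Control patients excluded from this population". They have no 24-week peak VO2, so none is regression-imputed. ITT minus FASB (Tables XII.1a and XII.7a, means of ten imputations), for the six Control patients:
- baseline (10.910×213 − 10.883×207)/6 = 11.84
- 24-week (10.727×213 − 10.745×207)/6 = 10.11

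A fall of 8.59 appears in ITT5 and ITT10 and is gone in FASB; the largest fall in a Control completer is 4.99. Responders are 281 − 279 = 2 of 60 (3.3%) in Control and 380 − 369 = 11 of 70 (15.7%) in Optimizer. FASB10 Control is taken as 33, because the printed 15.94% of 207 is 33, not the printed 30.

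**7. Full population.** Mean ITT responders are 28.1/213 and 38.0/215, a difference of 4.5 points. Approximate one-sided P under re-imputation from aggregates:
- 0.16: Case 6 donors removed, draw still free of baseline (27% responding in Cases 4 and 5, 20% in Cases 1 to 3)
- 0.12: every patient in Cases 1 to 5 at the pooled completer rate of 14.7%
- 0.07: the same patients at their own arm's completer rate
- 0.05: no responder in Cases 4 and 5 (20% in Cases 1 to 3)

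None is below 0.025.

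**8. Subgroups.** EF≥25 as imputed: 24.2/117 − 11.4/113 = 10.6 points. Own-arm completer rates give 10.0 to 11.7 with 18 or 0 Case 6 patients per arm in the subgroup. EF≥25/NYHA III as imputed: 23.4/109 − 9.1/97 = 12.1, against 12.4 to 14.7 on the same basis. The subgroup split of Case 6 is not published; unequal splits widen the ranges to 8.8–12.9 and 11.3–15.8.

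**The case against.** The strongest reply is that nothing reported is shown to change. ITT and completers (P = 0.0932) both miss 0.025. Completed-case results, free of donor draws, are reported for both subgroups (P = 0.0230 and P = 0.0073). All of this stands, although those results leave out every imputed or assigned patient.

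The size of the fault is easy to overstate, and four inferences should not be drawn.

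- That 27% of outcomes are affected. 428 − 313 = 115 lack an observed change, but that count includes the 36 Case 6 and 30 regression-imputed patients. The donor step concerns 50.
- That the six Control patients measure the effect of omitting baseline AT. A draw free of baseline should average about 10.6 to 10.8 if Case 6 scores average 8 to 10 (assumption). The recovered 10.11 is lower, by roughly two to three of its standard errors (0.26). The identical 8.59 fall in two imputations may itself be a donated worst score. Some of the six may be Case 6. The completer benchmark for them is 11.42 or 11.35, depending on which baseline mean is used.
- That responder rates rose from 18% to 26%. That is a normal approximation, and the 13 patients without follow-up lie below it in both arms. Cases 1 to 5 together average about 24.6% and 26.3%, but that pools regression and donor imputation and takes Case 6 as non-responders.
- That the scheme favoured the device. The documents do not fix the direction.

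Two further points count for the report. Treatment group is in the score, although the text does not say whether draws were made within arm. Age, MLWHFQ, NYHA class and LVEF are also in it, and their correlation with AT is not given, so baseline is largely rather than wholly ignored. Protocol Section IX.D already calls for a worst-case analysis; that gives a bound but does not replace a plausible imputation. Table IX.1 is titled as coming from a separate statistical analysis plan that is not among the documents, so the scheme may have been prespecified. That would not correct the description of the pool.

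**Conclusion.** The point holds as a fault of method and description, not as a demonstrated bias. Baseline AT is absent from Table IX.3 although it meets the report's own availability rule. The stated 348 donors with actual data cannot be right: at least 21 lack an observed 24-week AT on any reading, and the case counts and footnote 8 identify the pool as 312 complete cases plus 36 Case 6 patients. The 4.10 minimum in two imputations indicates that assigned scores were donated. That the correlation is largely lost rests on the missing AT term and on an independence approximation for the score.

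The two faults act in opposite directions on responder rates and cannot be separated from aggregates. The full-population conclusion is unchanged in every scenario tried. For EF≥25 and EF≥25/NYHA III the net effect on the imputed results is unknown; a reader might infer that those results are overturned, and the documents do not support that. With one of them reported at P = 0.0260, the check is still worth making.

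The MAR footnote claims more than non-significant baseline tests can show.

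**What to change.** - Beside the existing scheme, report a sensitivity analysis labelled post hoc for ITT, EF≥25 and EF≥25/NYHA III. Impute 24-week AT within arm by multiple imputation or predictive mean matching conditional on baseline AT, with peak VO2, RER, exercise duration and week-12 AT where available. Only patients with an observed 24-week AT donate. Case 6 patients keep their assigned scores but do not donate.
- Describe the existing donor pool as Case 0 plus Case 6, give the number with an observed 24-week AT, and state whether draws were within arm.
- Reword the Table IX.1 footnote to say that baseline comparisons cannot establish MAR.

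The cost is some extra analysis with standard software on data already held, plus short text corrections. The drawback is that the method is chosen after results are known, so it supplements the original analysis and does not replace it.
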